number of participants in each of two groups: intervention group (132) and control group (usual care) (132). Since participants will be recruited from only four regions, we will model the effect of region as a fixed effect rather than a random effect.¹⁸ This will allow region-specific intervention effects to be modelled (i.e. region by intervention interaction effects). If no region by intervention interactions are found, the interaction terms will be dropped from the model and we will estimate an overall intervention effect. Since the region by intervention interaction is unknown, we take a conservative approach with a sample size calculation that will enable detection of an intervention effect within each site. This will allow for a properly powered analysis of the site by treatment interaction. The primary outcome measure (Transition Readiness Assessment Questionnaire, TRAQ)⁹ has been validated on a sample of youth with congenital heart disease and in the absence of literature specific to BBD, we will base our sample size calculations on these findings. We anticipate a mean TRAQ self-management baseline score of 3.01 (SD 1.02) (out of a possible 5.0) as reported for youth (with congenital heart disease) without a transition intervention and an anticipated mean score of 4.0 at 6 months post-intervention resulting in a change score of 1 (i.e., 1 SD), with $\alpha=0.05$ and 90% power.¹⁹ Therefore, in each region, we will require 23 youth in each of the 2 arms (total of 46) x 4 regions = 184. Estimating 30% attrition, we will enroll 264 participants.

Inclusion Criteria

- Youth with chronological age between 15 and 17 years of age (i.e. before 18th birthday), in one of the four study regions, followed in pediatric care and for whom a discharge from pediatric care is planned but not for at least 6 months.
- A diagnosis of one of the following neurological BBD: autism spectrum disorder, cerebral palsy, epilepsy, spina bifida, or fetal alcohol spectrum disorder.
- Cognitive ability to provide informed consent and the ability to read and understand English or French
- Access to internet and a smartphone, iPad/tablet or desktop computer.
- TRANSITION-Q²⁰ score >40 (as a screen to define a minimum threshold for transition readiness based on our earlier work).

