During the course of study participation, participants will receive regular reminder messages and/or monthly phone calls to promote the use of the MyREADY Transition™ BBD App and to assist with troubleshooting any problems accessing the intervention. The App uses local storage within the device and synchronizes each participant's progress information with the Content Management System (CMS) which is hosted by Amazon and managed jointly by a software company (RootQuotient) and the Research IT team at McGill University. The Research IT team at McGill University will send regular reports to the RAs and/or the RCT Coordinator to monitor when key time points are achieved (e.g. when a participant has completed at least 25%, 50%, 75% and 100% of the App content, or when it has been more than 2 weeks since a participant has accessed the App).

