While TRAQ measure refinement is ongoing, and other versions are now available, our sample size calculation is based on findings from an intervention trial¹⁹ where the 29-item version of the TRAQ was used. The 29-item version has a Self-management domain (16 items) and a Self-advocacy domain (13 items). Each item is scored 1-5, where 1 = “No, I do not know how” and 5 = “Yes, I always do this when I need to.” The TRAQ will be completed by youth participants in both groups at Baseline and at 6-Months. It takes 5-10 minutes to complete.

Utilization of Intervention (Usage, Adherence, and Fidelity)

We will use mixed methods to assess MyREADY Transition™ BBD App usage, adherence and fidelity, and to identify the barriers and facilitators to using the IT platform for users.

Quantitative Data: We will track and analyze quantitative measures of App use for all components of the IT platform using two approaches:

1. MyREADY Transition™ BBD App will include support for utilization data gathering that can be used during the intervention and evaluation phases of the project. For example, it will log data related to end user login to the system (times and dates), section/session/video views (including sub-section features), challenge completion, access to games at the arcade, time spent on a section/session and trends over time. In addition, we will track and assess sections/sessions/videos progress by patient condition and/or other user variables by referencing information from the user profile. Within the App, users are asked to provide

NOTE: CTO#1666 Amendment approved by HiREB on January 9, 2023. Target sample was 264 participants; however, we randomized 52 participants, and did not complete the full-scale RCT. Linking health card numbers with provincial administrative data is labour intensive and costly, and the small number would not provide meaningful results. As approved by ethics, we dropped the health economic outcome analysis (Health card number linking, Health Utilities Index (HUI), Resource Use Questionnaire (RUQ)) and destroy stored health card number data.

optional feedback at the end of each section. Thus, we can track and analyze the extent and frequency of use, and the profiles of patients who did or did not use the IT platform. This information will be exported to Excel and will also be presented in a website dashboard (“Compliance Dashboard”).

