We will request consent to obtain youth participant's Health Card Number to answer questions about use of health services like physician office visits, visits to emergency rooms and hospitalizations during

NOTE: CTO#1666 Amendment approved by HiREB on January 9, 2023. Target sample was 264 participants; however, we randomized 52 participants, and did not complete the full-scale RCT. Linking health card numbers with provincial administrative data is labour intensive and costly, and the small number would not provide meaningful results. As approved by ethics, we dropped the health economic outcome analysis (Health card number linking, Health Utilities Index (HUI), Resource Use Questionnaire (RUQ)) and destroy stored health card number data.

the study period (between the time a participant joins the study up until March 31, 2021). Participants have the option of participating in the study without sharing the youth's Health Card Number. The Health Card Number will allow us to link the information provided in the study with provincial data regarding the participant's use of health services. We will work with appropriate organizations in each province (Alberta, Ontario, Quebec, New Brunswick, and Nova Scotia) to gain approval to access provincial Health Services Administrative Data repositories. Health care services data recorded in the provincial administrative databases will be linked deterministically to the study data using the Health Card Number, partial date of birth and sex.

STATISTICAL ANALYSIS:

We will use regression analysis to adjust for baseline function as a sensitivity analysis to address any residual imbalance from the randomization.

The analysis and reporting of the internal pilot phase and main RCT results will follow CONSORT guidelines²³⁻²⁴. Patient demographics and baseline outcome variables (both primary and secondary) will be summarized using descriptive summary measures. All analyses will be performed using SAS 9.4 (Cary, NC). Analysis will be intention to treat. The table below provides a summary of study objectives, corresponding outcomes, hypotheses and methods of analyses. For subgroup analysis we will use interaction test (interaction of subgroup variable with the treatment or intervention variable).

Table 1: Study Objectives, Corresponding Outcomes, Hypotheses and Methods of Analyses

Objective	Outcome	Criterion for Success	Method of Analysis

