Primary: To determine whether the MyREADY Transition™ BBD App intervention will result in improved transition readiness	Primary: 
 Change in TRAQ self-management score from Baseline to 6 months. 	Intervention > Control	T-Test; p<0.05
	Secondary: 
 Change in TRAQ self-advocacy score from Baseline to 6 months. 	Intervention > Control	T-Test; p<0.05
	Secondary 
 Health care transition experience 	Individual semi-structured interviews	Qualitative Methods
Secondary: What is the effect of the MyREADY Transition™ BBD App intervention for	Primary: Population Health 
 Serious illness (hospitalizations, ICU admission questions from Resource Use Questionnaire 	Intervention > Control	T-Test for continuous outcomes Chi-square test

NOTE: CTO#1666 Amendment approved by HiREB on January 9, 2023. Target sample was 264 participants; however, we randomized 52 participants, and did not complete the full-scale RCT. Linking health card numbers with provincial administrative data is labour intensive and costly, and the small number would not provide meaningful results. As approved by ethics, we dropped the health economic outcome analysis (Health card number linking, Health Utilities Index (HUI), Resource Use Questionnaire (RUQ)) and destroy stored health card number data.

improving health and use of health systems?	
 • PedsQL™ Pediatric Quality of Life • Patient Activation Measure (PAM) (health-related self-efficacy) • TRANSITION-Q 		for hospitalization
	Secondary: 
 • Utilization MyREADY Transition™ BBD App 	User metrics built into MyREADY Transition™ BBD App intervention to assess the extent to which various components of the intervention are accessed	Descriptive
	Secondary: Cost utility/cost-effectiveness 
 • Health Utilities Index® (Hui2/3) • Resource Use Questionnaire 	Evaluate changes in patients' health in relation to changes in cost to assess if the intervention represents an efficient allocation of health care resources	Descriptive; Cost-effectiveness analysis with support from Child-Bright health economics network team

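### The primary TRAQ comparison is called intention to treat, but no rule covers youth without a 6-month score, so as written it would rest on those with both scores

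*Combined protocol and SAP*

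**What the plan says.** The Statistical Analysis section commits to a principle: "Analysis will be intention to treat". It does not define the analysis set or say what happens to a participant with no outcome.

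Table 1 gives the primary outcome as "Change in TRAQ self-management score from Baseline to 6 months", tested by a t-test at p<0.05. The Sample section also describes a model with region as a fixed effect and region-by-intervention terms, which are dropped if no interaction is found. The one sensitivity analysis named is a regression on baseline function, meant for chance imbalance after randomisation.

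Under Primary Measures: "The TRAQ will be completed by youth participants in both groups at Baseline and at 6-Months". There is no TRAQ assessment in between.

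The Sample section closes its calculation with "Estimating 30% attrition, we will enroll 264 participants". Under Intervention and Control Conditions, participants get "regular reminder messages and/or monthly phone calls to promote the use" of the App. The note repeated through the document says that 52 youth were randomised against a target of 264 and that the health economic analysis was dropped. It does not alter the TRAQ analysis.

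**The concern.** A change score needs both values. A youth with no 6-month form has none, so an unimputed t-test on change leaves that youth out. The region model and the baseline-adjusted regression would do the same unless a missing-data method is added. The planned loss is large, and enlarging the sample to allow for it protects power only.

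At stake is the question the trial asks. The Synopsis describes a pragmatic trial of whether the intervention works under usual conditions, so youth who disengage belong to the target of inference. Participants know their allocation, and contact about App use falls on the App arm. It is therefore plausible that loss differs by arm, in rate or in how it relates to outcome. A comparison of completers would then not estimate the effect of offering the App, and a larger sample would not remove the error.

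**Working it through.** **1. The plan's own sample size.** Inputs from the Sample section: difference 1 (from 3.01 to 4.0, i.e. 0.99), SD 1.02, "with $\alpha=0.05$ and 90% power". The exact two-sided t-test calculation gives 22.87 per arm for a difference of 1, so 23, with 90.2% power. Four regions and two arms give 23 × 8 = 184. For 30% attrition, 23 / 0.70 = 32.9, so 33, and 33 × 8 = 264. The stated figure is reproduced and is not in dispute. It also shows that the trial was sized on the youth who remain.

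**2. How many lack a 6-month score.**
- Planned: 264 × 0.30 = 79.2, leaving 184.8 (about 185).
- Actual: 52 × 0.30 = 15.6, leaving 36.4 (about 36, or 18 per arm). This assumes that the planned rate applies and that the arms are equal in size.

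**3. Bias of the completer comparison.** In one arm let d be the share lost, C the completers' mean change, and C − g the leavers' mean change. The mean over all randomised is (1 − d)C + d(C − g) = C − d·g. The completer difference therefore exceeds the all-randomised difference by

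bias = d(App) × g(App) − d(control) × g(control).

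The documents give no loss by arm and no shortfall g, so the values below are assumptions.

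**4. Standard error.** SE = 1.02 × √(1/n1 + 1/n2). The SD of 1.02 is the baseline figure, taken as the SD of change as the sample size calculation does.
- 132 × 0.7 = 92.4 per arm: SE = 0.150.
- 26 × 0.7 = 18.2 per arm: SE = 0.338.
- With 40% and 20% loss: 0.152 and 0.342.

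**5. Results.** Rejection rate when the App has no true effect = Φ(−1.96 + bias/SE) + Φ(−1.96 − bias/SE).

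| Loss App / control | Shortfall App / control | Bias (TRAQ points) | Rejection, about 185 analysed | Rejection, about 36 analysed |
|---|---|---|---|---|
| 30% / 30% | 0.5 / 0.5 | 0 | 5% | 5% |
| 30% / 30% | 0.5 / 0 | 0.30 × 0.5 = +0.15 | 17% | 7% |
| 40% / 20% | 0.5 / 0.5 | 0.20 − 0.10 = +0.10 | 10% | 6% |
| 20% / 40% | 0.5 / 0.5 | 0.10 − 0.20 = −0.10 | 10% | 6% |
| 40% / 20% | 0 / 0 | 0 | 5% | 5% |

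The last row shows that unequal loss alone does no harm if it is unrelated to outcome. The +0.15 case is about 15% of the planned 0.99 (0.15 / 0.99). It equals one standard error at the planned size, but 0.15 / 0.338 = 0.44 of one at the actual size.

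**The case against.** **The documents never say complete case.** A reader might infer that the plan contradicts itself by prescribing a completer analysis. That goes too far: Table 1 names a test, not a dataset, and a t-test can be run on imputed data. What stands is that no missing-data method appears anywhere, so an analyst with only this text would use youth with both scores.

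**The t-test is not the only model described.** Correct: the Sample section has the region model. It has no missing-data rule either.

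**The direction is not known.** A reader might infer that the App effect is overstated because low App users leave. The documents do not support this. They plan to interview youth who completed little App content, after the 6-month data point, and the App-arm survey at the end of the intervention asks about reasons for not using the App. Non-use is thus treated as distinct from loss to follow-up. The reminders and calls could as well keep App-arm youth in the study, which would favour the 20% / 40% row.

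**Loss may be smaller than planned.** The 6-month package can be completed online, by mail or by phone, and youth in both arms receive gift cards. These may reduce loss, but the plan still expects 30%, and they do not handle what is lost.

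**Imputation from baseline data would not remove the bias in the worked example.** This also stands. If App-arm leavers fall short for reasons unrelated to baseline variables, imputing them from App-arm completers with similar baselines gives them the completers' gain, and the +0.15 remains. Only sensitivity analyses that depart from missing at random address that case.

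**Conclusion.** The point holds as a gap with a definite consequence. Intention to treat is promised, nothing says how a missing 6-month score is handled, and the stated methods used as they stand give an estimate from youth with both scores. The 30% expected loss is the plan's own figure.

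Bias is a risk, not a finding. It needs loss related to outcome, and a difference between arms in the rate of loss or in that relation. Under the assumed values it runs from −0.10 to +0.15 TRAQ points in the worked cases, and it is zero when loss and shortfall match. Nor should a reader conclude that 16 of the 52 were lost, since actual attrition is not reported.

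At the planned size such bias could raise the false-positive rate from 5% to about 10% to 17%. With about 36 analysed the figure is about 6% to 7%, and imprecision is the larger problem. The possible shift in the estimate is no smaller, though, and an estimate from a small trial may inform later work. The change is worth making, but it does not rescue the precision of the comparison.

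**What to change.** - Define the primary comparison as all randomised youth in the arm to which they were assigned.
- Replace the change-score t-test with ANCOVA of 6-month TRAQ self-management on arm, baseline TRAQ and region (the randomisation stratum). Handle missing 6-month scores under missing at random, by a small imputation model or a likelihood-based model. State that this does not correct loss related to the unseen outcome; with baseline variables only, imputation adds little to the ANCOVA itself.
- Pre-specify two sensitivity analyses for that case: missing App-arm outcomes imputed from the control arm, and a tipping-point shift of the imputed scores (for example from 0 to −1.0 TRAQ points) applied to each arm, since bias can go either way.
- Report 6-month missingness by arm with reasons, and the logged App use of App-arm leavers. This would show whether leavers were in fact low users.
- Keep the completer t-test as supportive.

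The cost is plan wording and modest programming in SAS 9.4, with no new data, visits or participants and no change to the stated sample size. Intervals may be wider. With about 18 completers per arm (assuming 30% loss), the imputation model must stay very small: fitting several covariates and four regions separately by arm would be fragile.

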Pediatric health care providers are encouraged to talk to children and youth about taking on more responsibility for their own health as they mature. Yet many providers report that they do not have the time, resources or helpful tools, nor do they have engaging ways to talk about making a smooth move to the adult system. This study proposes to overcome these barriers by applying interventions based on individual functional needs to promote transition readiness (self-management and self-advocacy skills) through an innovative e-health intervention. The overall objective of this project is to improve readiness for transition of care in youth with BBD who are between 15 and 17 years of age, are beginning to manage their own or have the potential for self-management.

We acknowledge the input from youth, parent/caregiver and health care stakeholders, who emphasized that a youth's transition to adulthood involves many systems beyond health care. In this study, however, we focus primarily on health care transition. Transition from pediatric to adult health care systems is a critical turning point for a growing population of youth with lifelong conditions. When the transition to adult health care is unplanned or poorly supported, patients' and parents'/caregivers' adverse experiences of care are higher, as is risk for poor health outcomes, costly hospitalizations, inequity of health care services, and "other" costs such as missed school or work³.

Patient-centred care and patient engagement have become central components of the modern clinical encounter. Enhancing patient engagement via information technology is shown to directly impact patient behaviour that promotes positive health outcomes, patient satisfaction, care delivery efficiency, reduces costs and improves quality of care and patient safety.⁴⁻⁵

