The COPM is an evidence-based, generic, and individualized outcome measure used to capture a client's self-perception of performance and satisfaction in everyday living, over time.²⁷ The measure accomplishes this by identifying problems in performing activities of daily living. The patient is encouraged to think about things that they want to do, need to do or are expected to do but can't do, don't do or aren't satisfied with the way they do. Concrete examples are provided for youth: things related to their health and personal care, getting ready for the day, getting around, working, household chores, school, recreation, socializing. The patient is asked to rate current performance of each using a 10-point scale from 'not able to do it' to 'able to do it very well'. The patient is also asked to rate satisfaction with performance on a 10-point scale from 'not satisfied at all' to 'extremely satisfied' with higher scores reflecting better performance and satisfaction with performance as perceived by the patient. The performance and satisfaction can be re-assessed following a period of treatment.²⁸ The COPM will be administered to all youth participants.

TRANSITION-Q²⁰

The TRANSITION-Q is a 14-item transition readiness/self-management ability scale.^{20, 29} This short, clinically meaningful and psychometrically sound scale can be used in research and in pediatric and adolescent clinics to help evaluate readiness for transition.²⁰ Item responses ("never" = 0, "sometimes" = 1, and "always" = 2) are summed to create a raw score, with a possible range from 0 to 28. Raw scores are transformed using a table provided by the developers and the transformed scores range from 0-100. A higher score indicates greater transition readiness; exhibiting more self-management skills with higher frequency.^{20, 30}

A TRANSITION-Q score > 40 will be used as an eligibility screen to define a minimum threshold for transition readiness based on our earlier work. At the point of screening and recruitment, we will evaluate several components of cognitive function as well as youth capacity to share the management of their own health. The TRANSITION-Q screen will inherently exclude youth who have severe intellectual disability, and/or those who rely significantly on parents/caregivers in most areas of daily functioning, self-care and/or communication. We will repeat the TRANSITION-Q at the 6-Month Follow-Up Visit.

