PedsQL™ Pediatric Quality of Life Instrument, Generic Core, Teen Report (13-18 years)¹¹

The PedsQL™ Measurement Model (http://www.pedsql.org/about_pedsql.html) is a modular approach to measuring health-related quality of life (HRQOL) in healthy children and adolescents and those with acute and chronic health conditions.

In this study the PedsQL™ Pediatric Quality of Life Instrument, Generic Core, Teen Report (13-18 years) will be completed by youth participants at Baseline and 6-Months. The form is brief (23 items), practical (less than 4 minutes to complete), multidimensional (Physical, Emotional, Social, School Functioning), reliable (Child Self-Report; 0.90) and valid (Distinguishes between healthy children and children with

NOTE: CTO#1666 Amendment approved by HiREB on January 9, 2023. Target sample was 264 participants; however, we randomized 52 participants, and did not complete the full-scale RCT. Linking health card numbers with provincial administrative data is labour intensive and costly, and the small number would not provide meaningful results. As approved by ethics, we dropped the health economic outcome analysis (Health card number linking, Health Utilities Index (HUI), Resource Use Questionnaire (RUQ)) and destroy stored health card number data.

acute and chronic health conditions; distinguishes disease severity within a chronic health condition), and responsive to clinical change over time.

Patient Activation Measure (PAM) (health-related self-efficacy)³¹

The Patient Activation Measure (PAM) (<http://www.insigniahealth.com/products/pam-survey>) is a valid, reliable, unidimensional, Guttman-like scale based on a developmental model of activation. Activation appears to involve four stages: (1) believing the patient role is important, (2) having the confidence and knowledge necessary to take action, (3) actually taking action to maintain and improve one's health, and (4) staying the course even under stress. The measure has good psychometric properties indicating that it can be used at the individual patient level to tailor intervention and assess changes.³¹

PAM originally included 22 questions, and through subsequent validation of the short-version now has 13 questions. The PAM assesses a patient's confidence in self-managing their condition, and the total score allows individuals to be categorized into four levels:

Level 1 - disengaged and overwhelmed

Level 2 - becoming aware, but still struggling

Level 3 - taking action

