Level 4 - maintaining behaviours and pushing further

PAM has been used as a measure of health-related self-efficacy in a relevant study of transition to adult care among adolescents with chronic disease utilizing a technology program.³² Hibbard et al.³³ reported on the relationship between increased patient activation and improved self-management.

The license with Insignia Health for the PAM Measure does have a data-sharing requirement for scoring purposes. This is necessary to score each survey as there is not a scoring algorithm or rubric that is a static formula.

Health Care Experience

Measure of Process of Care (MPOC) (family-centred care)³⁴

The Measure of Processes of Care (<https://canchild.ca/en/resources/47-measure-of-processes-of-care>) is a well-validated and reliable self-report measure of parents' perceptions of the extent to which the health services they and their child(ren) receive are family-centred. The original version of MPOC is a 56-item questionnaire; as of 1999 there is a shorter, 20-item version. MPOC has been used internationally in many evaluations of family-centred service. Parents/caregivers will complete the MPOC-20 at Baseline and 6-Months. Additional mixed methods questions related to satisfaction with service will be complement the information collected within the MPOC.

Newest Vital Sign³⁵

As a complement to our Baseline measures, we will include a health literacy measure called Newest Vital Sign (NVS) <http://www.pfizer.com/health/literacy/public-policy-researchers/nvs-toolkit>. It is appropriate for our population and research purpose and can be easily administered in 3 minutes. The NVS measures words and numbers, not just word recognition. Since the NVS was published in December

NOTE: CTO#1666 Amendment approved by HiREB on January 9, 2023. Target sample was 264 participants; however, we randomized 52 participants, and did not complete the full-scale RCT. Linking health card numbers with provincial administrative data is labour intensive and costly, and the small number would not provide meaningful results. As approved by ethics, we dropped the health economic outcome analysis (Health card number linking, Health Utilities Index (HUI), Resource Use Questionnaire (RUQ)) and destroy stored health card number data.

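### Does Table 1's shared success criterion point the wrong way for hospitalisation and ICU admission?

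*Combined protocol and SAP*

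**What the plan says.** The Statistical Analysis section introduces Table 1 with the words "The table below provides a summary of study objectives, corresponding outcomes, hypotheses and methods of analyses". Under the secondary objective, the Population Health row names four outcomes. The first is "Serious illness (hospitalizations, ICU admission questions from Resource Use Questionnaire"; the others are PedsQL, PAM and TRANSITION-Q. The entry in the success-criterion column is "Intervention > Control". The methods are a t-test for continuous outcomes and a chi-square test for hospitalisation. The row runs over a page break, so that one criterion covers all four outcomes is the natural reading rather than an explicit statement.

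The objective for the row is "improving health and use of health systems". For the scales, the Study Measures section says of TRANSITION-Q that "A higher score indicates greater transition readiness". It describes PAM as rising from "Level 1 - disengaged and overwhelmed" to "Level 4 - maintaining behaviours and pushing further". It does not give the scoring direction of PedsQL. The serious-illness questions are described under the Resource Use Questionnaire heading as an addition to a modified subset of that questionnaire.

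The January 2023 note, repeated throughout the document, reports that 52 participants were randomised and that the health economic outcome analysis was dropped. It names the Resource Use Questionnaire among the items removed.

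**The concern.** Three of the four outcomes in the row are scales on which a larger value is, or may be assumed to be, the better one. Serious illness runs the other way: more hospitalisations or ICU admissions is worse. A single greater-than sign cannot be right for both kinds of outcome if it is read as a numerical inequality. No footnote defines the sign as meaning better, and nothing reverse-codes the serious-illness item.

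A chi-square test does not carry a direction of its own, so the criterion column is the only place in the analysis plan where a direction for this outcome appears. If someone applied the table mechanically, a higher admission rate in the App arm would be labelled a success and a lower one a failure. What is at stake is that label, for one non-primary outcome.

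**Working it through.** **Direction of each outcome against the criterion.**

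| Outcome in the row | Better direction | Source | Fits "Intervention > Control" literally? |
|---|---|---|---|
| TRANSITION-Q | Higher | Study Measures | Yes |
| PAM | Higher | Study Measures, Levels 1 to 4 | Yes |
| PedsQL | Higher (assumed; not stated) | None | Yes, on that assumption |
| Serious illness | Lower | Background and Rationale | No |

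The last line rests on the document's own rationale. It says that after an unplanned or poorly supported transition adverse experiences of care are higher, "as is risk for poor health outcomes, costly hospitalizations, inequity of health care services".

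**What the literal reading does.** The documents give no event rate, so the risks here are assumed. With 5% in the App arm and 10% in control, the difference is 0.05 − 0.10 = −0.05: a benefit that fails the criterion. Reversing the arms gives +0.05: a harm that meets it. With 10% and 20% the differences are −0.10 and +0.10, with the same result.

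**Whether the sign enters any test.** It would do so only if tests were one-sided. The plan does not state sidedness, but its sample size shows it. For a difference of 1 SD, alpha 0.05 and 90% power:

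- Two-sided: n per arm = 2 × (1.960 + 1.282)² / 1² ≈ 21.0, so 22 by the normal approximation, and 23 by the exact t calculation.
- One-sided: n per arm = 2 × (1.645 + 1.282)² / 1² ≈ 17.1, so 18, and still 18 by the exact t calculation.

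The plan states 23 per arm per region, which matches the two-sided test. Then 23 × 2 × 4 = 184. With 30% attrition, 23 / 0.70 = 32.9, rounded up to 33, and 33 × 8 = 264, the stated enrolment.

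For hospitalisation the named test is chi-square, which squares the difference. Take 26 per arm (52 / 2) with 0 events in one arm and 4 in the other:

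chi-square = 52 × (0 × 22 − 26 × 4)² / (26 × 26 × 4 × 48) = 562,432 / 129,792 = 4.33, p = 0.037.

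Swapping the arms changes only the sign inside the square, so the statistic and p-value are the same. The estimated risk difference comes from the counts and does not depend on Table 1.

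**Whether the outcome is still live.** Table 1 takes serious illness from the Resource Use Questionnaire, the measures section describes the questions under that questionnaire, and the January 2023 note drops it. The natural reading is that the item is no longer analysed. The note does, however, describe what was dropped as the health economic analysis, while Table 1 places serious illness under Population Health, apart from the cost-effectiveness row.

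**The case for a change.** The best case for a correction starts from the TRAQ rows. There the same symbol is a numerical inequality: the hypothesis in Study Aims and Hypothesis is that App users will have higher change scores, and Table 1 writes this as "Intervention > Control". A reader could fairly expect the symbol to mean the same thing in the next row. The table is presented as giving the hypotheses, the test supplies no direction, and the amendment note does not say in terms whether the serious-illness questions were kept. Mending one row would cost almost nothing.

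Most of this stands as description. The literal sign does not fit the outcome, that the sign is shorthand for better is likely but not proven, and the status of the item after the amendment is not spelled out.

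What does not stand is the step to a consequence. The criterion column is not used as a formal decision rule throughout: other entries in it name interviews, describe usage metrics, or state the purpose of the economic evaluation. The introduction calls the table a summary. With an objective about improving health and a rationale that counts hospitalisation as a harm, no analyst would report excess ICU admissions as a success.

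**Conclusion.** A clerical slip, and no gain from acting on it. The shared criterion is the wrong sign for serious illness if read literally, but calling the hypothesis reversed would overstate it, since the objective and the background fix the intended direction. The effect is confined to the success label of one non-primary outcome. It is zero on every estimate, p-value and sample-size figure, and on the TRAQ conclusion.

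This rests on two-sided testing, which the stated 23 per arm supports, and on higher PedsQL scores being better, which the documents do not state. It does not depend on how the January 2023 note is read. If the questions were dropped with the questionnaire, the entry is a leftover with no analysis behind it. If they were kept, the analysis runs as written and its result is read in the obvious direction.
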